7.3 Treatment Assignment

Patients will be randomized 1:1 to receive open-label treatment with SEL-212 or KRYSTEXXA.

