7.4.1 Safety Criteria for Adjustment or Stopping Doses

7.4.1.1 SEL-212

A patient randomized to treatment with SEL-212 will be withdrawn from study drug for meeting the following stopping rule:

- In the SEL-212 arm: SUA level > 1.0 mg/dL measured at the Day 21 visit of Treatment Period 1 or SUA level > 6.0 mg/dL at the Day 21 visit of Treatment Periods 2, 3, 4, or 5

The window for all Day 21 visits is -2/+1 days.

If a Day 21 visit SUA value drawn within the protocol window is not available, but if a SUA value drawn at an unscheduled visit after the Day 21 window is available prior to dosing that is ≤ 1.0 mg/dL during Treatment Period 1 or ≤ 6.0 mg/dL during Treatment Periods 2, 3, 4, or 5, the patient will not be required to be withdrawn from study drug and may be eligible to receive their subsequent dose.

If 1) a Day 21 visit SUA value drawn within the protocol window is not available and no subsequent SUA results are available or 2) a Day 21 visit SUA value drawn within the protocol window is not available and a subsequent SUA drawn at an unscheduled visit after the Day 21 window is > 1.0 mg/dL during Treatment Period 1 or > 6.0 mg/dL during Treatment Periods 2, 3, 4, or 5, then the patient will be withdrawn from study drug based on the protocol deviation.

If withdrawn from study drug, the patient will continue study visits to the end of Treatment Period 6. At the discretion of the Investigator, the patient will be permitted to return to urate lowering therapy 60 days after the patient's last study drug treatment. Urate lowering therapy shall not be SEL-212 or KRYSTEXXA.

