13.1 Sample Size Determination

The primary efficacy criterion in this study is defined as the percentage of subjects who achieve and maintain reduction of SUA < 6 mg/dL for at least 80% of the time during Treatment Period 3 and Treatment Period 6.

The percentage of responders according to the above criterion is assumed to be 65% in the SEL-212 arm and 44% in the KRYSTEXXA arm.

Using the Chi-square test for comparison between the SEL-212 arm and the KRYSTEXXA arm, and considering a one-sided alpha=5% and the statistical power of 80%, results in 69 subjects per treatment group. Taking into account that some subjects may be excluded from the modified Intent-to-Treat (mITT) analyses (Section 13.2.4), 75 subjects per treatment group will be randomized. For the sample size estimation, Chi-square test, instead of the Cochran-Mantel-Haenszel test, is used although the randomization will be stratified for tophus presence (yes/no) as there is no valid assumption of the distribution of this stratification variable within the eligible subject population.

Sample size calculations were performed with the software package nQuery Advisor® Sample Size Calculator V. 8.2.1.0.

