5.5. Per Protocol Set

The Per Protocol (PP) Set will include all patients who 1) were administered any amount of study medication, and 2) have completed at least 65% of the study dosing visits with or without receiving study drug (eg at least 4 of 6 TP Day 0 visits for patients receiving SEL-212 or at least 8 of 12 TP Day 0 or Day14 visits for patients receiving Krystexxa) unless early termination from the study occurred after study drug withdrawal due to meeting stopping rules or due to an adverse event, or due to PI discretion (for example where at least one pre-dose SUA was >6 mg/dL in the Krystexxa arm and patient was discontinued from study treatment), and 3) who have no major Protocol deviations affecting the primary efficacy assessments. Patients will be analyzed according to randomized treatment.

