5.6. Protocol Deviations

All protocol deviations related to study inclusion or exclusion criteria, conduct of the trial, patient management, dosing, and sampling procedures or patient assessment will be listed. The list of protocol deviations will be reviewed by the Sponsor, the principal investigator, the study statistician and the study pharmacokineticist and finalized before database lock. Determination of whether the deviation is major or minor, or has impacts on primary efficacy assessment will be based on the biasing impact of the deviation on the safety and efficacy data. Major protocol deviations affecting the primary efficacy assessments include: 1) major protocol deviations that lead to premature study drug discontinuation; 2) major protocol deviations that lead to patients receiving study drug treatment in treatment periods 3 or 6 that they would not otherwise have received (such as incorrect application of the protocol stopping rules that allow a patient to continue dosing despite having met the stopping criteria); and 3) protocol deviations that involve out of window sampling of SUA due to a) visits occurring outside of the protocol visit window for dosing days (where dosing days refer to dosing visits of patients still on study drug who have not previously been withdrawn from study drug) in Treatment period 3 and 6, b) visits occurring outside of the protocol visit

This document is confidential.

window for visits within TP3 or TP6 scheduled 1 week prior to the dosing days, c) visits occurring outside of the protocol visit window for TP6 D21 for patients who have not been withdrawn from study drug and for dosing day TP4D0, or d) visits occurring 35 days or more beyond TP6D0 for the TP6D28 visit for patients who have not been withdrawn from study drug, where the protocol visit window above refers to the current protocol window allowed at the time of analysis. Major protocol deviations affecting the primary efficacy assessments will be reviewed and determined periodically during clinical and medical review of protocol deviations during the study.

Protocol deviations related to Covid-19 will be identified and flagged.

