The estimator for the comparison between the treatment groups is defined as the difference in the proportion of responders between patients receiving SEL-212 versus those receiving KRYSTEXXA® during Treatment Periods 3 and 6. The statistical testing will be performed confirmatory using the Cochran-Mantel-Haenszel (CMH) test – considering the randomization stratum of tophus presence (yes/no) – with a one-sided type 1 error rate $\alpha = 5\%$. In addition, 90% two-sided confidence intervals for the overall treatment difference between SEL-212 and KRYSTEXXA® treatment groups without stratification will be computed. The analysis of the estimands will be carried out based on the ITT primarily. Supportive analyses will be performed on the mITT and the PP.

A logistic regression model to compare treatment difference controlling for presence of tophus will be performed as supportive analysis.

In addition, a sensitivity analysis will be performed as below for the primary endpoint:

- If a subject withdraws from study treatment before completing period 6 due to stopping rules met for treatment, the subject will be considered as a non-responder for the primary efficacy endpoint.
- If a subject withdraws from the study before completing period 6 or the study terminates prior to a subject completing period 6, the primary efficacy endpoint is based on SUA assessment for period 3 where $T1$ be the total time interval in hours for Treatment Period 3 of which $W1$ hours is the time interval during which SUA level is < 6 mg/dL:

$$\text{Percentage (p)} = \frac{W1}{T1} \times 100$$

Summary tables of the percentage of responders (patients who achieve and maintain reduction of SUA < 6 mg/dL for at least 80% of the time) will be provided by treatment group. Additionally, a summary table with the total time a patient has SUA values < 6 mg/dL will be provided for treatment period 3 and treatment period 6 by treatment group.

Summary tables of the actual values and change from baseline for SUA results will be provided for each scheduled sampling time point by treatment group.

This document is confidential.

Additionally, mean SUA level, reduction in mean SUA and percent reduction in mean SUA from baseline during Treatment Periods 3 and 6, during Treatment 3, and during Treatment Period 6 will be summarized by treatment group respectively and will be compared for treatment difference using ANOVA model with presence of tophus and treatment group as fixed factors

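### After a missed Day 21 sample, a SEL-212 patient's place in the per-protocol set and the stopping-rule analyses can depend on whether the later SUA is high or low

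*Protocol*

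**What the plan says.** **SEL-212 withdrawal (Protocol 7.4.1.1).** An in-window Day 21 SUA above the threshold (1.0 mg/dL in Treatment Period 1, 6.0 mg/dL in Periods 2 to 5) meets the stopping rule. If there is no in-window value, a later unscheduled value at or below the threshold lets the patient continue. If the later value is above it, or no later value exists, "then the patient will be withdrawn from study drug based on the protocol deviation".

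**Krystexxa withdrawal (Protocol 7.4.1.2).** Two consecutive pre-dose values above 6.0 mg/dL meet the stopping rule. No clause labels an SUA-driven withdrawal a deviation.

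**PP set (Protocol 13.2.5, SAP 5.5, SAP 5.6).** Criterion 3 requires that there be no major deviation affecting the primary efficacy assessments. SAP 5.6 lists first among these "major protocol deviations that lead to premature study drug discontinuation". Item 3(b) adds out-of-window visits in Periods 3 and 6 that fall one week before dosing. Criterion 2, the 65% dosing-visit rule, excuses patients who left the study after stopping drug for a stopping rule, an adverse event or investigator discretion, "for example where at least one pre-dose SUA was >6 mg/dL in the Krystexxa arm".

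**Uses of the stopping-rule label.** The SAP 7.1 sensitivity analysis makes a patient a non-responder who "withdraws from study treatment before completing period 6 due to stopping rules met for treatment". SAP 6.1 has stopping-rule Kaplan-Meier curves, and SAP 8.1 compares stopping-rule rates between arms with a CMH test.

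**Role of PP.** It is supportive for the primary endpoint (SAP 7.1) and stands beside ITT for the SUA secondary endpoints (SAP 7.2.1).

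**The concern.** Two SEL-212 patients miss the same Day 21 window. One has a low late SUA, keeps dosing and stays in PP. The other has a high late SUA, is withdrawn under a deviation label and may leave PP. What separates them is the variable on which efficacy is judged. An analysis set selected in this way loses failures from the SEL-212 denominator, and no Krystexxa clause produces a matching loss.

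The label also matters outside PP. The sensitivity analysis and the stopping-rule summaries are meant to capture loss of SUA control that ends treatment. A withdrawal for a documented high SUA that is filed as a deviation falls outside those definitions, although the same value drawn in window would count. SAP 7.4.1 itself expects COVID-19 to disrupt the study, so missed windows are plausible.

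**Working it through.** **1. The plan's own figure.** Inputs from Protocol 13.1: response "assumed to be 65% in the SEL-212 arm and 44% in the KRYSTEXXA arm"; "considering a one-sided alpha=5% and the statistical power of 80%, results in 69 subjects per treatment group"; "75 subjects per treatment group will be randomized". With pooled variance and no continuity correction:

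n = [1.645·√(2 × 0.545 × 0.455) + 0.842·√(0.65 × 0.35 + 0.44 × 0.56)]² / 0.21² = 68.5, rounded up to 69 per arm. The stated figure is reproduced, and these inputs serve for the illustration in step 4.

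**2. Same missed window, two outcomes (SEL-212).**

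| | Late SUA at or below threshold | Late SUA above threshold |
|---|---|---|
| Dosing | may continue | withdrawn, as a deviation |
| PP, Periods 1, 2, 4, 5 | stays | leaves if the deviation is graded major |
| PP, Period 3, late Day 21 visit | listed under item 3(b) | listed under item 3(b) |
| SAP 7.1 stopping-rule non-responder rule | not triggered | not triggered |

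Selection on the result therefore arises in Periods 1, 2, 4 and 5. In Period 3, item 3(b) applies whatever the value.

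**3. Sensitivity analysis.** Take a SEL-212 patient controlled throughout Period 3 who has a late SUA above 6.0 in Period 4 or 5, is withdrawn from drug, and then leaves the study before completing Period 6. The second part of the SAP 7.1 sensitivity analysis scores this patient on W1/T1 from Period 3 alone. That can be 80% or more, which makes a responder. With the same value in window, the first part makes the patient a non-responder. The primary analysis also makes the patient a non-responder, because the study was left before Period 6 was completed.

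**4. Illustrative size in PP.** Let k be the number of SEL-212 non-responders removed from 75, with nobody removed from Krystexxa. The documents do not give k, so 1 to 8 is an assumed range. Apparent SEL-212 rate = (rate × 75)/(75 − k). At 65% the numerator is 48.75; at 44% it is 33.

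| k | Rate if truly 65% | Difference from 44% | Rate if truly 44% | Spurious difference | One-sided type I error in PP |
|---|---|---|---|---|---|
| 0 | 65.0% | 21.0 | 44.0% | 0.0 | 5.2% |
| 1 | 65.9% | 21.9 | 44.6% | 0.6 | 5.9% |
| 3 | 67.7% | 23.7 | 45.8% | 1.8 | 8.1% |
| 5 | 69.6% | 25.6 | 47.1% | 3.1 | 10.9% |
| 8 | 72.8% | 28.8 | 49.3% | 5.3 | 16.0% |

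The last column comes from exact binomial enumeration of the pooled z-test at 44% in both arms, ignoring the tophus strata.

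**5. Are the removed patients non-responders?** The illustration assumes so. With two 28-day periods, response needs 0.80 × 56 = 44.8 days below 6 mg/dL. A patient controlled for all 28 days of Period 3 and then withdrawn still needs 16.8 of 28 days (60%) in Period 6 while off study drug. Returning to urate-lowering therapy makes the patient a non-responder in the primary analysis. The assumption is reasonable but not certain.

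**The case against.** Several objections stand and limit the point.

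- **The exclusion is conditional.** SAP 5.6 speaks of major deviations, grades them by biasing impact, and nowhere says that a missed Day 21 sample is always major. Removal from PP is a possible outcome of review. That is still a reason to settle it by rule, since the trial is open-label.
- **The scope is narrow.** A high in-window Day 21 value is an ordinary stopping-rule withdrawal. In Period 1 the threshold is 1.0 mg/dL, so a late value between 1.0 and 6.0 is not loss of control on the endpoint's own 6 mg/dL scale.
- **Krystexxa patients are not expressly kept in PP.** A reader might infer from the Krystexxa example that patients stopped after one high value are retained in that arm alone. The text does not support this. The investigator-discretion clause is an exception to the visit-attendance criterion, its wording covers both arms, Krystexxa is only the example, and it does not override criterion 3.
- **Other analyses still capture these patients.** The all-cause treatment-discontinuation Kaplan-Meier curve in SAP 6.1 includes them. Those who stay in the study are still assessed on their SUA in the sensitivity analysis.
- **A careless fix would reverse the bias.** Keeping only late-high Period 3 patients in PP, while item 3(b) excludes late-low ones, would select against SEL-212.

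What does not stand is that this is only missing detail. Where the deviation is graded major, the rules as written make PP membership depend on the result.

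**Conclusion.** The concern holds in a limited form. For SEL-212 patients without an in-window Day 21 SUA in Periods 1, 2, 4 or 5, a high late value can remove the patient from PP while a low one does not. Krystexxa has no corresponding clause. The deviation label also puts these withdrawals outside the sensitivity analysis's stopping-rule criterion, and they may be missed in the stopping-rule Kaplan-Meier and CMH summaries.

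It would be tempting to conclude that the trial's main result is tilted towards SEL-212. The documents do not support that: ITT is the primary set, it keeps these patients, and the SUA secondary endpoints are also analysed on ITT.

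The size cannot be derived from the documents. Under the assumptions that k non-responders of 75 are removed, none is removed from Krystexxa, and PP otherwise equals all randomized patients, the SEL-212 rate rises by about 0.9 points for each patient removed (65% to 69.6% at k = 5). The change should be made before database lock, but it does not threaten the primary analysis.

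**What to change.** For analysis only, with conduct and thresholds unchanged:

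1. In SAP 5.6, 6.1, 7.1 and 8.1, classify a SEL-212 withdrawal with a documented SUA above the protocol's own threshold, in or out of window, as an SUA-driven (stopping-rule) withdrawal. State that the unscheduled result may be used for this, because SAP 5.7 otherwise leaves unscheduled data to listings.
2. Do not exclude such a patient from PP under the first SAP 5.6 item. Count the patient as a failure in the sensitivity analysis and in the stopping-rule summaries.
3. Apply item 3(b) to out-of-window Period 3 Day 21 visits in the same way whether the SUA is high or low.
4. Leave withdrawals with no later SUA as deviations; they are not selected on a high value.
5. Reconcile Protocol 7.4.1.1, the PP definition (Protocol 13.2.5 and SAP 5.5) and SAP 5.6, so that the analysis class and the conduct label do not conflict.

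Rewording the investigator-discretion example is optional, since the clause already applies to both arms. The cost is a few SAP sentences and a reconciliation with the protocol text. No new data are needed.

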7.4.1.2 KRYSTEXXA

A patient randomized to treatment with KRYSTEXXA and who has started receiving treatment with study drug will be withdrawn from study drug for meeting the following stopping rule:

- In the KRYSTEXXA arm: SUA level > 6.0 mg/dL measured on 2 consecutive pre-dose measurements, based on the following assessments:
 - If a pre-dose SUA level is > 6.0 mg/dL, then the Investigator will have the option to schedule a second SUA measurement to occur 2 days before the next scheduled KRYSTEXXA dosing day. The pre-dose SUA collected on Day 0 of Treatment Period 1 shall not be used in determining whether to invoke the stopping rule.
 - If the second measured SUA level is > 6.0 mg/dL, then the Investigator will withdraw the patient from study drug per the stopping rule.

- If the second measured SUA level is ≤ 6.0 mg/dL, the patient can proceed to dosing with KRYSTEXXA. However, SUA will be assessed on the day of dosing, per protocol, to be used determining consecutive pre-dose measurements for future stopping rules.

If withdrawn from study drug, the patient will continue study visits to the end of Treatment Period 6. At the discretion of the Investigator, the patient will be permitted to return to urate lowering therapy 60 days after the patient's last study drug treatment. Urate lowering therapy shall not be SEL-212 or KRYSTEXXA.

7.4.2 Criteria for Adjustment or Stopping Doses

An independent Data and Safety Monitoring Committee (DSMC) will be formed by charter to assist in reviewing safety data and may provide recommendations to the Sponsor regarding study drug dose adjustment or study termination.

7.5 Criteria for Study Termination

The study can be terminated at any time at the Sponsor's sole discretion. Otherwise, the study will be terminated when all patients have completed follow-up assessments ([Section 20](#)) or the Sponsor or regulatory agency(ies) have determined there is an unacceptable risk to patients or additional dosing or procedures are not warranted or necessary.

The study may be terminated at a particular investigational site under the following conditions:

- The Investigator fails to enroll patients at an acceptable rate;
- The Investigator fails to comply with pertinent regulations;
- There is insufficient adherence (i.e., compliance) to the protocol;
- Knowingly false information is submitted to the IRB, Sponsor or designee, or regulatory authorities.

7.6 Study Rationale

7.6.1 Rationale for the Study Design

Study SEL-212/202 is a randomized, open-label, parallel-arm study to compare the safety and efficacy profiles of SEL-212 to KRYSTEXXA.

A randomized, controlled study is the gold-standard for evaluation of efficacy in clinical research. Randomized, controlled studies are quantitative, comparative, controlled experiments in which treatment effect sizes may be determined with less bias than observational trials. Randomization is considered the most powerful experimental design in clinical trials: with other variables equal between groups, on average, any differences in outcome can be attributed to the intervention.

The study will be conducted on an open-label treatment basis; therefore, all patients, Investigators, study personnel, and Sponsor personnel involved in the conduct of the study will

have access to the randomized treatment assignments. Only the assessments of qualitative endpoints (health questionnaires and joint assessment) will be conducted on an assessor-blinded basis. The open-label design was selected because of the substantial differences in administration of SEL-212 and KRYSTEXXA (Section 10) and the practicality of maintaining the treatment blind. The parallel arms involving active treatment will permit adequate statistical comparison of the groups for efficacy and safety signal detection.

KRYSTEXXA was selected as the active comparator because it is approved for this patient population and because the exogenous protein carries similar risks to the SEL-037 component of SEL-212.

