9.4 Randomization and Blinding

This is a randomized, open-label treatment study. Patients will be randomized 1:1 to receive SEL-212 or KRYSTEXXA. Randomization preferably should occur 7 days prior to the first dose of study drug (ie, Day -7). The randomization will be stratified for tophus presence (yes/no). Assessments of qualitative endpoints will be conducted on an assessor-blinded basis.

Prior to study drug administration in Treatment Periods 2 through 6, the Investigator will determine a patient's eligibility for treatment with study drug by evaluating the patient's SUA level measured from the blood sample obtained from Day 21 of the most recently completed Treatment Period (SEL-212 cohort) or from the previous 2 measurements (KRYSTEXXA cohort).

Study personnel will endeavor to safeguard the integrity of the qualitative endpoint blind to minimize bias in the study.

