11.3 Health Questionnaires: Patient Reported Outcomes and Quality of Life Assessment

11.3.1 Health Assessment Questionnaire-Disability Index (HAQ-DI)

The HAQ-DI will be administered according to the schedules described in [Section 20](#).

The HAQ-DI, which includes the patient global assessment and pain scale, is an instrument that assesses fine movements of the upper extremity, locomotor activities of the lower extremity, and activities that involve both the upper and lower extremities. Standard scoring takes into account the use of aids and devices or assistance from another person. There are 20 items in 8 categories that represent a comprehensive set of functional activities: dressing, rising, eating, walking, hygiene, reach, grip, and usual activities. The stem of each item assesses a patient's functional ability using their usual equipment during the past week. Each category contains at least 2 specific sub-category questions. For example, under the category "walking," patients are asked about their ability to walk outdoors on flat ground and to climb up 5 steps.

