11.3.3 Short Form Health Survey 36 (SF-36)

The SF-36 will be administered according to the schedules described in [Section 20](#).

The SF-36 is a 36-item scale constructed to survey health status and quality of life ([Ware 1992](#)). The SF-36 assesses 8 health concepts: limitations in physical activities because of health problems; limitations in social activities because of physical or emotional problems; limitations in usual role activities because of physical health problems; bodily pain; general mental health (psychological distress and well-being); limitations in usual role activities because of emotional problems; vitality (energy and fatigue); and general health perceptions. The standard form of the instruments asks for patients to reply to questions according to how they have felt over the previous week.

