3.6. Treatment Assignment & Blinding

This is a randomized, open-label treatment study. Patients will be randomized 1:1 to receive SEL-212 or KRYSTEXXA®. Randomization preferably should occur 7 days prior to the first dose of study drug (ie. Day -7). The randomization will be stratified for tophus presence (yes/no). Assessments of qualitative endpoints will be conducted on an assessor-blinded basis.

SEL-212 is comprised of 2 components: SEL-037 and SEL-110.36 with dose level 0.15 mg/kg and 0.2 mg/kg respectively based on patient's weight. The dose level for KRYSTEXXA® is 8 mg (uricase protein).

Study personnel will endeavor to safeguard the integrity of the qualitative endpoint blind to minimize bias in the study.

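### HAQ-DI and SF-36 are described as assessor-blinded, but their rater is the unblinded patient and their only baseline follows randomization

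*Protocol*

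**What the plan says.** Protocol 7.6.1 explains that the trial is open-label, so that "all patients, Investigators, study personnel, and Sponsor personnel involved in the conduct of the study will" "have access to the randomized treatment assignments". The next sentence reads: "Only the assessments of qualitative endpoints (health questionnaires and joint assessment) will be conducted on an assessor-blinded basis". The same assurance appears in the protocol synopsis, 7.1, 7.1.2 and 9.4 and in SAP 3.3 and 3.6. SAP 3.6 gives its purpose: "Study personnel will endeavor to safeguard the integrity of the qualitative endpoint blind to minimize bias in the study".

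Protocol 11.3 lists three health questionnaires.
- **HAQ-DI** (11.3.1): "The HAQ-DI, which includes the patient global assessment and pain scale, is an instrument that assesses fine movements" and it rates the patient's functional ability over the past week.
- **SF-36** (11.3.3): "The standard form of the instruments asks for patients to reply to questions according to how they have felt over the previous week".
- **PrGA** (11.3.2): a provider's rating of disease activity.

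On timing, Protocol 7.1.2 randomizes patients before Baseline, and Protocol 9.4 prefers Day -7. Quality of life is first assessed on Day 0 of Treatment Period 1; Appendices A and C schedule no questionnaire at Screening or Day -7. SAP 5.8 defines baseline as the last value before infusion starts. SAP 7.2.2 to 7.2.4 analyse change from that value by ANCOVA, with the same value as covariate. Protocol 13.4.2 makes all secondary tests one-sided at 5%.

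**The concern.** Assessor blinding protects an outcome when the person who forms the judgement does not know the arm. For a patient-reported score that person is the patient, and the protocol says patients have access to the assignment. For HAQ-DI and SF-36 the plan therefore states a safeguard that its own design does not provide against the rater's knowledge.

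Baseline adds a second route. A covariate measured after randomization in an open-label trial is no longer guaranteed to be independent of assignment. Here it is both the reference for change and the adjustment variable.

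What is at stake is how a set of one-sided secondary comparisons may be read. A reader who accepts the blinding statement would give the quality-of-life results more weight than open-label patient-reported outcomes deserve.

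**Working it through.** **1. Plan's own figure.** The documents give no number on this point. The only computed design figure is 69 per arm for the primary endpoint (65% vs 44%, one-sided 5%, 80% power). It reproduces with the pooled chi-square formula: (1.645 × √(2 × 0.545 × 0.455) + 0.842 × √(0.65 × 0.35 + 0.44 × 0.56))² / 0.21² = 68.5, rounded up to 69. It concerns laboratory serum uric acid and is not in dispute.

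**2. Who rates what.**

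| Outcome | Rater | Can a blinded assessor hold? |
|---|---|---|
| HAQ-DI | patient | no, not against the patient's own knowledge |
| SF-36 | patient | no, same reason |
| PrGA | provider | yes, if that provider is kept from the assignment |
| Joint counts | examiner | yes, on the same condition (tenderness still depends partly on the patient's response) |

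**3. How many comparisons.** SAP 7.2.2 to 7.2.4 compare 1 HAQ-DI total + 8 SF-36 domains + 2 SF-36 components + 1 PrGA = 12 scores. Patient-rated: 1 + 8 + 2 = 11. SAP 4.2 asks for change to the end of Treatment Periods 3 and 6, so 11 × 2 = 22 comparisons.

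**4. Order of events.** Randomization (preferably Day -7), then the first and only pre-treatment questionnaire (Day 0), then infusion. No section withholds the arm until the Day 0 form is complete, and none says when the patient is told.

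**5. How bias would travel.** Let b be the between-arm shift in reported baseline and f the shift at follow-up, both caused by knowing the arm, with no true effect. Unadjusted change is biased by f - b; ANCOVA with baseline slope β is biased by f - βb.
- Follow-up only (b = 0, f = d): bias d either way.
- Baseline only (b = d, f = 0): size d for the change score and βd for ANCOVA.
- Same shift at both times (b = f = d): 0 for the change score and (1 - β)d for ANCOVA.

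**6. Illustration.** The documents give no SD, correlation or bias size. I assume d from 0.1 to 0.3 SD, ρ from 0.5 to 0.7, equal variances (so β = ρ), 75 per arm and bias favouring SEL-212. The false-positive rate is Φ(bias / (σ√(2/75)) - 1.645), with σ = √(1 - ρ²). Example for d = 0.2 and ρ = 0.5: 0.2 / (0.866 × 0.163) = 1.414, and Φ(-0.231) = 41%.

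| Shift d | Follow-up only, ANCOVA | Baseline only, ANCOVA | Same shift at both: ANCOVA bias |
|---|---|---|---|
| 0.1 SD | 17–22% | 10–15% | 0.03–0.05 SD |
| 0.2 SD | 41–53% | 17–33% | 0.06–0.10 SD |
| 0.3 SD | 68–82% | 28–56% | 0.09–0.15 SD |

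With no shift the rate is the nominal 5%; a shift the other way lowers it. The follow-up route is the larger of the two, and no choice of baseline date removes it.

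**The case against.** **No patient blinding is claimed.** The protocol is openly open-label, and assessor blinding can be read as applying to whoever administers and scores the forms. This stands in part: a blinded administrator can limit interviewer influence, and the statement can be true for PrGA, which is one of the health questionnaires. A reader might infer that the assurance is empty altogether; the documents do not support that. For HAQ-DI and SF-36, however, the stated aim of minimizing bias is not met where it matters most.

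**The timing is inferred.** A reader might conclude that patients rate their baseline a week after learning their arm. The documents say only that randomization precedes Baseline, preferably at Day -7. Knowledge by Day 0 is likely in an open-label trial but is not stated.

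**The direction is unknown.** Both arms are active, so a reader should not infer that the bias favours SEL-212. If the same shift persists to follow-up, moving baseline before assignment raises the bias, from 0 to d for the change score and from (1 - β)d to d for ANCOVA. This stands, and it is why the baseline move is secondary.

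**An earlier baseline costs more than a week's age.** Both instruments look back one week. Washout of urate-lowering therapy and colchicine each start at least 7 days before Baseline, and exclusion 7 makes the week before first dose largely flare-free. A Day -7 recall week can precede all of this. That stands, but it applies equally to both arms.

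**It may be too late.** Protocol version 3.0 is dated 08 June 2020, with last completion estimated at 31 July 2020. Subtracting 168 treatment days puts the last Day 0 near 14 February 2020. On those estimates most or all baselines already exist. This limits the baseline change but not the wording change.

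**The stakes are limited.** These are secondary endpoints with no hierarchical order (SAP 7.2), and SAP 7.2.2 to 7.2.4 make no blinding claim of their own. That reduces the weight of the point but leaves the incorrect statement in place.

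**Conclusion.** The point holds as an incorrect blinding statement for two instruments. HAQ-DI and SF-36 are open-label patient-reported outcomes, and calling them assessor-blinded is wrong as written. It affects how 11 of the 12 questionnaire scores can be read. That their only baseline is post-randomization is also confirmed; that patients know their arm when they complete it is an inference.

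The amount of bias is not established. The rates shown rest on assumed shifts, correlations and direction, and indicate only that modest reporting shifts would matter for one-sided 5% tests with 75 per arm.

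Two broader readings are not supported. The primary serum uric acid endpoint is not touched. Gout flares are not misdescribed either, because Protocol 7.6.1 limits the blinding claim to questionnaires and joint assessment.

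**What to change.** 1. In the protocol synopsis, 7.1, 7.1.2, 7.6.1 and 9.4, and in SAP 3.3 and 3.6, restrict the assessor-blinded statement to joint counts and PrGA.
2. In SAP 7.2.2 and 7.2.4, state that HAQ-DI and SF-36 are open-label patient-reported outcomes and that their one-sided comparisons are supportive.
3. For any patient not yet randomized, collect baseline HAQ-DI and SF-36 before the assignment is released, and name that value as baseline in SAP 7.2.2 and 7.2.4. Otherwise a Day 0 form, if also completed, would replace it under SAP 5.8. For all other patients, disclose that the baseline was taken after randomization.

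**Cost.** Items 1 and 2 are text only, and the quality-of-life results are described less favourably. Item 3 changes Appendices A and C, may apply to few or no patients, and can leave two kinds of baseline in one analysis. Its recall week can also fall before washout and colchicine start. It does not remove reporting bias at follow-up, so items 1 and 2 are needed in any case.
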